7.3. Sensitivity Analyses for Primary Variable

7.3.1. Sensitivity Analyses Under Various Assumptions for Missing Values

The sensitivity analyses specific for non-EMA regions include the following supportive estimand:

- EMA-Estimand using MAR and MNAR MI methods using ITT population to impute the missing values

The sensitivity analyses specific for EMA region include the following supportive estimands:

- Non-EMA-Estimand using MMRM with mITT population
- EMA-Estimand using MAR MI methods to impute the missing values using ITT population

For both non-EMA and EMA regions, an estimand similar to EMA-Estimand with population changed to mITT population will be used for sensitivity analyses, and missing values imputed by MAR and MNAR MI methods separately.

7.3.2. Subgroup Analysis

The treatment effect of the pridopidine active group vs. placebo will be evaluated for the primary endpoint in participant subgroups according to the following variables at Baseline:

- Age categorized into three groups (<55, 55 to <65, and ≥65 years)
- Sex (Male vs Female)
- Randomization strata: HD stage (HD1 vs HD2)
- Randomization strata: Baseline neuroleptic use (Y/N)
- Region (North America, Europe)
- CAG repeats categorized into 2 groups by median Baseline CAG
- The CAG-Age-Product (CAP) score calculated as: age *(CAG – 33.66), and categorized into two groups by median Baseline CAP
- Four groups based on crossing median Baseline CAP and median Baseline age
- Baseline NfL categorized into 2 groups by median Baseline NfL
- Concomitant use of medication for Chorea management

Subgroup analyses by median will use the median in the ITT population irrespective of the population analyzed.

The primary model for subgroup analyses will contain main effects and 2-factor interactions Treatment x Week and Treatment x Subgroup to determine the p-value. The structure of the covariance matrix will follow the same approach as indicated for the primary endpoint.

Assessment of impact of subgroups on efficacy will be evaluated by the interaction between Treatment x Subgroup.

For each subgroup (assuming not already in the primary model), the MMRM model under MAR will be estimated for each subgroup level to determine the treatment effect and CI. When analyzing HD1 vs HD2, the randomization stratification factor of HD stage will not be included in the MMRM model. The same applies to subgroups of neuroleptic use.

The LSM and SE of the LSM change from Baseline for each treatment group, and the 95% CI for the comparisons (pridopidine 45 mg bid vs. placebo) will be presented for each subgroup along with the p-value for the interaction term.

If a subgroup has <50 participants in any Treatment a subgroup analysis may not be performed since there would be less reliable comparison between the treatment groups.

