3.3. Sample Size and Power Considerations

Based on experience with early HD participants in the prior Phase 2 PRIDE-HD study, we expect the difference in mean change from Baseline to Week 65 between the 45 mg bid treated and placebo groups to be 0.7 points on the UHDRS-TFC with a standard deviation (SD) of 1.9 points.

A total sample size of 372 participants will provide 94% power to detect a between-group difference of 0.7 points in the mean change from Baseline to 65 weeks in the UHDRS-TFC score, with an SD of 1.9 points, using a two-tailed t-test at a significance level of 0.05. Assuming a drop-out rate of 22.5%, a total of 480 participants will be randomized. The sample size was calculated using SAS version 9.4 PROC POWER.

Based on feedback from Regulatory Authorities, the power assessment was updated as below. Assuming a dropout rate of 22.5 % in each treatment group early in the study, under assumption of Missing Not at Random (MNAR) with imputed values for all discontinued participants estimated based on the trajectory of placebo participants with available data, we anticipate a difference in change from Baseline to imputed values at Week 65 for this group to be 0.1 points. The overall difference would then be 0.565 (0.7*0.775+0.1*0.225) or 0.7 points for the 77.5% completers and 0.1 points for the 22.5 % participants who discontinue and have imputed data at Week 65. A difference of 0.565 points with SD of 1.9 with a sample size of 480 participants would provide 90% power (SAS V 9.4 PROC POWER).

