7.3.3. Other Efficacy Analysis

To explore potential impact of other confounding factors on efficacy, the primary efficacy endpoint, select secondary and exploratory endpoints analyses may be conducted if there are enough participants in these cohorts.

Following sensitivity analyses may be performed, where applicable:

- Similar to non-EMA-Estimand with population changed to Week 65 PP Population
- Non-EMA Estimand with an additional covariate, CAP score, included in the analysis model
- EMA-Estimand with an additional covariate, CAP score, included in the analysis model
- A sensitivity analysis excluding those who had received any neuroleptics during the study that could impact efficacy may be performed.
- In addition, further sensitivity analysis may be conducted excluding those who had changes in neuroleptic use after randomization.

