To investigate the additional covariates that may have an effect on change in NfL over time, more covariates will also be added one at a time or altogether to the above model: CAG repeats, age, sex, CAP score, BMI, region, Baseline UHDRS-TFC, Baseline cUHDRS, Baseline Q-Motor [REDACTED] Baseline UHDRS-TMS, Baseline SDMT, and Baseline SWR. When all covariates are added to the model together, a stepwise model selection approach (specifically, a variable needs to be significant at the level of 0.25 to enter the model during the first forwardstep and to be significant at the level of 0.10 to remain in during the second backwardstep) will be adopted in order to see the most influential covariates on the change in NfL over time. Each covariate will be tested at a type I error level ≤ 0.05 , two-sided and the 95% two-sided CIs of the effect estimates will be computed.

- (2) To investigate how Baseline NfL, as a covariate, impacts change from Baseline to Weeks 26, 52, 65 and 78 in efficacy endpoints including UHDRS-TFC, cUHDRS, Q-Motor [REDACTED], UHDRS-TMS, SDMT, and SWR accounting for the effect of pridopidine 45 mg bid vs placebo.

The main analysis is based on the change from Baseline in UHDRS-TFC, cUHDRS, Q-Motor [REDACTED] UHDRS-TMS, SDMT and SWR over time. Each dependent

variable will be fit by one model. Similar analyses will be repeated for actual values of the endpoints.

Analysis will be performed on observed data using MMRM separately for actual values and change from Baseline. The model will include the following effects: *treatment*, *categorical weeks*, *Baseline value of efficacy endpoint to be analyzed*, *Baseline log₂(NfL)*, randomization stratification factors (*HD stage* and *neuroleptic use at Baseline*), interaction effects of *treatment*categorical weeks*, and *treatment*Baseline log₂(NfL)*. The spatial power covariance matrix for repeated observations within participants will be used. The denominator degrees of freedom for the tests of fixed effects will be approximated by Kenward-Roger method.

Baseline log₂(NfL) and its interaction with other factors will be tested at a type I error level ≤ 0.05 , two-sided and the 95% two-sided CI of the parameters will be computed.

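### CAG, CAP and age are tested as effect modifiers only in categories; a continuous treatment-by-covariate test should be added beside them, as the SAP already does for baseline NfL

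*SAP*

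**What the plan says.** SAP 7.3.2 defines the subgroups for the primary endpoint. Among them are "CAG repeats categorized into 2 groups by median Baseline CAG", CAP split at its median, four groups from crossing median CAP with median age, and age in three fixed bands (below 55, 55 to below 65, 65 and over). Medians are taken from the ITT population. The decision rule is: "Assessment of impact of subgroups on efficacy will be evaluated by the interaction between Treatment x Subgroup". SAP 7.4.3 carries the same subgroup analyses to the multiplicity-adjusted secondary endpoints.

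Elsewhere these variables enter in other ways:

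- SAP 7.3.3 lists "Non-EMA Estimand with an additional covariate, CAP score, included in the analysis model", and the same for the EMA estimand. No treatment-by-CAP term is stated.
- SAP 7.6 may explore PIN_HD, an index that contains CAG and age, but in categories.
- The models in SAP 9.1.2 may add CAG, CAP and age as covariates, with no treatment interaction stated.

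Baseline NfL is handled differently. It has a median split in SAP 7.3.2, and Objective (2) of SAP 9.1.2 also studies "how Baseline NfL, as a covariate, impacts change from Baseline to Weeks 26, 52, 65 and 78 in efficacy endpoints". That model has a treatment-by-baseline log2(NfL) term, and adjusted effects are shown at the median and the quartiles.

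**The concern.** A median split treats participants just below and just above the cut as different, and treats those near the cut and far out on the same side as alike. If the drug effect rises or falls steadily with genetic burden, this discards information that the trial has already collected. SAP 3.3 sizes the trial for the main effect and states no power for any interaction, so there is little information to spare.

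The plan is also incomplete in one respect that needs no modelling. CAG is an integer count, so some participants will probably sit exactly on the median. SAP 7.3.2 says which population supplies the median but not which group those participants join. The two choices give different groups and possibly different p-values.

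The SAP gives no reason for using a continuous term for NfL but not for CAG, CAP or age.

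**Working it through.** **Inputs from SAP 3.3.** The test is planned "using a two-tailed t-test at a significance level of 0.05". The assumed effect is "0.7 points on the UHDRS-TFC with a standard deviation (SD) of 1.9 points". The size statement is "A total sample size of 372 participants will provide 94% power to detect a between-group difference of 0.7 points", followed by "Assuming a drop-out rate of 22.5%, a total of 480 participants will be randomized". Allocation is 1:1 (SAP 3.4).

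**The plan's own figures reproduce.** With z = difference × √N / (2 × SD):

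- N = 372: 0.7 × √372 / 3.8 = 3.55, and Φ(3.55 − 1.96) = 94%.
- 372 / (1 − 0.225) = 480.
- N = 480: 0.565 × √480 / 3.8 = 3.26, and Φ(3.26 − 1.96) = 90%.

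**Information kept by a median split.** For a linear modifier X, the fraction kept is the squared correlation between X and the indicator of being above the median. For a normal X the correlation is √(2/π) = 0.798, so 2/π = 63.7% is kept. Then 372 participants act like 372 × 0.637 = 237, and 480 like 306.

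**Effect on power.** The continuous interaction has standard error 2 × 1.9 / √372 = 0.197 TFC points per covariate SD (0.173 at N = 480). A slope of 2.80 × 0.197 = 0.55 per SD gives 80% power. After the split, power is Φ(2.80 × 0.798 − 1.96) = 61%. From 90%, it is Φ(3.24 × 0.798 − 1.96) = 73%.

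**Dependence on shape.** The documents give no distribution for CAG or CAP, so every row is an assumption. Power is Φ(2.80 × √kept − 1.96).

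| Assumed shape | Kept | 80% becomes |
|---|---|---|
| Uniform | 75% | 68% |
| Normal | 64% | 61% |
| CAP built from assumed CAG and age | about 63% | 60% |
| Integer CAG, near-normal | 63–66% | 60–62% |
| Integer CAG, right-skewed | 56–64% | 55–61% |
| Lognormal, skewness about 1.8 | 52% | 52% |

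**Ties.** For an assumed rounded-normal CAG with mean 43 and SD 2.5, the upper group holds 58% of participants if ties go up and 42% if they go down.

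**Simulation (4,000 runs, N = 372).**

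| True modifier | Continuous test | Median split |
|---|---|---|
| Linear | 78% | 60% |
| Step at the median | 60% | 80% |
| None (type I error) | 5.5% | 5.3% |

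All power figures use a single Week 65 comparison with SD 1.9. The MMRM will give somewhat different absolute power, but the relative efficiency should be similar.

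**The case against.** The strongest counter-argument is that the advantage of the continuous test depends on the shape of the modification. If the drug works on one side of a threshold near the median, the planned split is the better test, by 80% to 60% in the simulation. Replacing it would therefore be a trade-off. This stands, and it is why the continuous test should be added and not substituted. A step exactly at the sample median is a special case, though, and the SAP gives no reason to expect one.

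The consequence is also limited. Subgroup p-values lie outside the testing sequence in SAP 5.6. SAP 7.3.2 also reports estimates and confidence intervals for each subgroup, so the interaction p-value is not the only evidence. This stands too.

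A reader might go further and infer that the split throws away up to 45% or more of the information, or that a real dependence on CAG or CAP will probably be missed because of it. The documents support neither. Losses that large need marked right skewness or, for an integer CAG, a skewed shape combined with the less favourable tie rule, and for CAP the loss is nearer 37%. In the worked example, power after the split is still 61% or 73%. For modest modification (0.3 points per SD), even the continuous test has only 33% power at N = 372 and 41% at N = 480, against 23% and 28% after the split. Low power there comes mainly from the size of the trial.

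**Conclusion.** The gap is real but minor. Effect modification by CAG and CAP is tested only after a median split, and by age only in categories. The SAP plans no continuous interaction for them, although it plans one for baseline NfL. Under a roughly linear modifier and a near-normal covariate, the split keeps about 64% of the information and lowers 80% power to about 61%. The chance of missing such an effect then rises from 20% to 39%.

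That size rests on two assumptions that the documents cannot settle: the covariate's shape (about 52% to 75% kept) and linearity (a step at the median reverses the ranking). No loss was computed for age. The missing tie rule for CAG holds without either assumption. Nothing here touches the primary analysis, its type I error or the secondary hierarchy.

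**What to change.** In SAP 7.3.2, beside the existing categorical analyses:

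- Prespecify an interaction of treatment with centred continuous CAG, and likewise with CAP and age, one model per variable.
- Check linearity with a quadratic or spline term.
- Show the estimated treatment effect at the quartiles, as SAP 9.1.2 does for baseline NfL.
- Keep the categories and their p-values.
- State on which side CAG values equal to the median fall.

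The cost is one extra model per variable, more exploratory p-values and a linearity assumption. The linearity check is itself weak in a trial of this size. No new data or alpha is needed. SAP section 5 allows the change by addendum before unblinding; after that it belongs in the CSR as a change to the planned analyses.

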7.3.3. Other Efficacy Analysis

To explore potential impact of other confounding factors on efficacy, the primary efficacy endpoint, select secondary and exploratory endpoints analyses may be conducted if there are enough participants in these cohorts.

Following sensitivity analyses may be performed, where applicable:

- Similar to non-EMA-Estimand with population changed to Week 65 PP Population
- Non-EMA Estimand with an additional covariate, CAP score, included in the analysis model
- EMA-Estimand with an additional covariate, CAP score, included in the analysis model
- A sensitivity analysis excluding those who had received any neuroleptics during the study that could impact efficacy may be performed.
- In addition, further sensitivity analysis may be conducted excluding those who had changes in neuroleptic use after randomization.

7.4. Multiplicity-Adjusted Secondary Efficacy Variable and Analysis

7.4.1. Key Secondary Efficacy Variable and Analysis

The key secondary efficacy variable is change from Baseline to Week 65 in cUHDRS. The null hypothesis is that pridopidine is no different than placebo in improvement of cUHDRS score at Week 65. The hypothesis testing will be based on the main cUHDRS estimand similarly defined as non-EMA-Estimand for primary endpoint (Section 7.2). Change from Baseline to Week 65 in cUHDRS will be analyzed using MMRM in the mITT population, under treatment policy strategy for handling missing data. The LSM and associated SE for change from Baseline in each treatment group, the 95% CI and p-value for the pridopidine treatment effect will be presented at Week 65.

The following sensitivity analyses will be performed for change from Baseline to Week 65 in cUHDRS:

- Analysis based on supportive estimand similar to EMA-Estimand for primary endpoint (Section 7.2) using MNAR imputation for missing values in the ITT population
- Analysis based on supportive estimand similar to EMA-Estimand for primary endpoint (Section 7.2) using MAR imputation for missing values in the ITT population
- Analysis based on supportive estimand similar to non-EMA-Estimand with population changed to W65PP population

7.4.2. UHDRS-TFC Response as a Binary Endpoint

The binary UHDRS-TFC response (yes or no) is defined as achieving improvement or no worsening in UHDRS-TFC score, i.e., change from Baseline to Week 65 in UHDRS-TFC ≥ 0

points. The responder analysis will be performed for the proportion of participants with change from baseline to Week 65 in UHDRS-TFC ≥ 0 .

The hypothesis testing to compare the percentage of responders between the two treatment groups will be based upon the mITT population. Logistic regression will be used to analyze and compare the probability of whether a participant is a UHDRS-TFC responder or not. The model will adjust for Baseline UHDRS-TFC, region, Baseline randomization stratification factors of neuroleptic use (Yes/No) and HD stage (HD1 and HD2).

The hypothesis testing of the UHDRS-TFC responder analysis is based on the main estimand as follows:

- Treatment: Pridopidine 45 mg bid or placebo (on background of standard of care) that participants are randomized to
- Population: Early HD Participants (HD1 & HD2) defined through the study inclusion/exclusion criteria. The mITT population will be used in analyzing this estimand
- Variable: Improvement or no worsening (change from Baseline ≥ 0 points) at Week 65 in UHDRS-TFC (Defined as responders to treatment)
- Population Level Summary: Proportion of responders, defined as the proportion of participants achieving improvement or no worsening in UHDRS-TFC (change from Baseline ≥ 0 points) at Week 65
- ICEs and Strategies for Addressing ICEs:

ICEs include treatment discontinuation and will be handled by combining composite strategy and hypothetical strategy as follows:

- Composite strategy: Observed UHDRS-TFC values will be used to determine if a participant is a responder or not. For treatment discontinuation due to disease-progression-related death, or meeting Stopping Rules, the participant will be considered a non-responder.
- Hypothetical strategy: For treatment discontinuation due to other reasons not included in composite strategy and no TFC data collected afterward, all values after ICEs will be imputed under MAR as if the participants had continued receiving the study treatment. The MAR imputation model will include UHDRS-TFC as a continuous response variable as described in Section 7.2. The UHDRS-TFC response at Week 65 (change from Baseline in UHDRS-TFC ≥ 0) will then be derived using the imputed UHDRS-TFC score as well as the non-missing UHDRS-TFC scores.

The odds ratio (OR) of treatment effect (pridopidine 45 mg bid vs placebo) along with a 2-sided 95% CI and p-value will be presented. An estimate of OR > 1 will indicate a beneficial treatment effect. Descriptive statistics and 95% CI using Clopper-Pearson will be provided for the observed proportions at each visit, along with the difference between treatment groups in the proportions and 95% normally approximated CI for the difference.

Following supportive estimands will be used to support the analysis of this secondary endpoint:

Supportive Estimand 1: similarly defined as the main estimand for UHDRS-TFC responder analysis, but with population changed to ITT population, and MNAR instead of MAR MI will be used under the hypothetical strategy.

Supportive Estimand 2: similarly defined as the main estimand for UHDRS-TFC responder analysis, but with population changed to ITT population.

Supportive Estimand 3: similarly defined as the main estimand for UHDRS-TFC responder analysis, but with ICE handling strategy changed to treatment policy strategy (using observed data without imputation).

Supportive Estimand 4: similarly defined as Supportive Estimand 3 for UHDRS-TFC responder analysis, but with population changed to W65PP population.

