under MAR as if the participants had continued receiving the study treatment. The MAR imputation model will include UHDRS-TFC as a continuous response variable as described in Section 9.4.2. The UHDRS-TFC response at Week 65 (change from Baseline in UHDRS-TFC \geq 0) will then be derived using the imputed UHDRS-TFC score as well as the non-missing UHDRS-TFC scores.

The proportion of participants with improvement or no worsening based on CGI-C (assessed as \geq 1 and \leq 4), will be analyzed using a logistic regression in the mITT population, as described above for binary UHDRS-TFC response.

Non-Multiplicity Adjusted Secondary Efficacy Endpoints:

The continuous non-multiplicity adjusted secondary endpoints (change from Baseline to post-baseline visits in UHDRS-TMS, Q-Motor [REDACTED] and cUHDRS total score) will be analyzed similarly as described in non-EMA-Estimand for the primary endpoint.

Q-Motor endpoints [REDACTED]

The binary non-multiplicity adjusted secondary endpoints, evaluated as proportion of participants meeting a given threshold, will be analyzed similarly to UHDRS-TFC response. Different thresholds that are clinically meaningful may be used for the responder analyses.

Further details for secondary analyses will be included in the SAP.

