7.1.1. Intercurrent Events (ICEs) and Estimand Strategy

The ICEs considered for the PROOF-HD trial include treatment discontinuation due to, for example, death, AEs, progressive disease, or meeting Stopping Rules for QT/CrCl/psychiatric reasons.

If a participant has COVID-19 symptoms, their visit can be delayed within a reasonable period (up to 4 weeks) to perform UHDRS-TFC and other efficacy and safety assessments until after their COVID-19 symptoms have resolved. There is also a low likelihood of participants stopping study drug or discontinuing from study due to COVID-19. If intermittent efficacy assessments are missing due to COVID-19 impact, it will be handled by analysis, such as MMRM, under MAR assumptions³.

Also, since pridopidine is taken over a long term (65 to 78 weeks) in the Main Study, temporary treatment interruptions are expected to have minimal impact on key efficacy endpoints.

ICH E9 R(1) describes five strategies to address ICEs (Mallinckrodt et. al., 2020; Ratitch et. al., 2020a and 2020b) which include:

- (1) **Treatment Policy** (similar to ITT principle) where the ICE is ignored;
- (2) **Composite** where the ICE is taken to be a component of the endpoint as in a responder analysis where participants who die due to disease progression are considered non-responders;
- (3) **Hypothetical** where hypothetical scenarios are considered in which the ICE did not occur such as excluding observations where the UHDRS was measured while the participant was exhibiting COVID-19 symptoms;
- (4) **Principal Stratum**, where the effect of the treatment is considered only in the stratum of interest such as excluding participants infected by COVID-19 anytime during the trial, and excluding participants on antipsychotics;
- (5) **While on Treatment**, where the response to the treatment prior to discontinuing treatment is of interest.

For the PROOF-HD trial we will use the treatment policy, composite, hypothetical strategies, and/or a combination of strategies to address the specific impact of ICEs on efficacy.

Based on the regulatory feedback, the main estimand for the primary endpoint, change from Baseline in UHDRS-TFC at Week 65, will be defined separately for the EMA and non-EMA regions.

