- For the EMA region, an estimand using a composite of treatment policy and hypothetical strategies is defined for the primary analysis. The treatment policy strategy will apply to all observed values including those collected after treatment discontinuation, and the hypothetical strategy will apply to missing values using ~~PMM~~ with control-based pattern imputation under MNAR assumptions (as described in Section 5.8.1.2).
- For the non-EMA regions, the primary analysis will be based on an estimand using treatment policy strategy, under which all observed data will be used regardless of occurrence of ICEs.

For the EMA region, the estimand applying treatment policy strategy (i.e., the primary estimand for the non-EMA regions) will be used as a supportive estimand, while for the non-EMA regions, the estimand applying a composite of treatment policy and hypothetical strategies (i.e., the primary estimand for EMA region) will be used as a supportive estimand.

The main estimands for secondary and exploratory endpoints will be the same for both EMA and non-EMA regions. The main estimand for key secondary endpoint, change from Baseline in cUHDRS at Week 65, will be based on treatment policy strategy and mITT population. The binary secondary endpoints, for example, the proportion of participants with improvement or no worsening in UHDRS-TFC, will use combined composite and hypothetical strategies for the main estimand. In this estimand, participants who discontinue the treatment due to disease progression-related death, or meet the Stopping Rules will be considered non-responders, while the participants who discontinue the treatment for other reasons will be imputed by hypothetical values from treatment discontinuation onward as if the participants had continued receiving the study treatment (MAR assumptions). A similar combined composite and hypothetical strategy estimand may be used for sensitivity analyses with MNAR MI under hypothetical strategy.

Other secondary and exploratory efficacy endpoints for both EMA and non-EMA regions, evaluated as changes from Baseline, will follow treatment policy strategy based estimand. Binary endpoints indicated for responder analyses will follow a similar estimand strategy as described above, where appropriate.

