7.4.3. Other Multiplicity Adjusted Secondary Efficacy Variable and Analysis

For continuous endpoints such as change from Baseline using observed data only, the main estimand will be similar to the non-EMA-Estimand for the primary endpoint, analyzed using the mITT population with treatment policy strategy to handle ICEs. An MMRM model as described in Section 7.2 for the primary endpoint will be used with Baseline value of the analyzed variable replacing Baseline UHDRS-TFC as a covariate. For the specified visits, the LSMs, SE of the estimates, p-values, and 2-sided 95% CIs will be provided for the within treatment group changes from Baseline and for the comparison of change from Baseline between pridopidine and placebo.

Supportive estimands for continuous endpoints will be similar to the EMA-Estimand for the primary endpoint, with population as the ITT population and missing values imputed using copy reference method under MNAR assumption. Additional missing value imputation approach under MAR assumption may be used as a sensitivity analysis.

For analysis of change from Baseline in UHDRS-TFC at Week 78, main analysis will include observed values at scheduled visits up to 78 weeks. A sensitivity analysis for Week 78 endpoints will be performed with assessments between Week 65 and 78 mapped to Week 78.

For positive response defined using values of continuous variables:

- Unless otherwise specified, where a decrease reflects disease progression, a responder will be defined as those with no change or improvement (change from Baseline ≥ 0)
- Unless otherwise specified, where an increase in score reflects disease progression, a responder will be defined as those with change from Baseline ≤ 0

Main estimands for binary endpoints will be similar to the main estimand for the binary UHDRS-TFC response, analyzed in the mITT population and with ICEs handled by a combined composite and hypothetical strategy. Supportive estimand for the binary endpoints will be similar to Supportive Estimand 1 for the binary UHDRS-TFC response. All responder analyses or analyses of binary variables will be performed using logistic regression as indicated for the binary secondary variable above in Section 7.4.1.

The p-values from the main estimand will be used in the hierarchical testing for multiplicity adjusted secondary endpoints following the order described in Section 3.2.2.

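### In the Week 65 UHDRS-TFC responder analysis, an mITT participant who dies of a cause unrelated to disease progression can be imputed as still on treatment and scored a responder

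*SAP*

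**What the plan says.** SAP 7.4.2 splits treatment discontinuations into two branches.

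- **Composite branch.** "For treatment discontinuation due to disease-progression-related death, or meeting Stopping Rules, the participant will be considered a non-responder".
- **Hypothetical branch.** "For treatment discontinuation due to other reasons not included in composite strategy and no TFC data collected afterward", the plan is that "all values after ICEs will be imputed under MAR as if the participants had continued receiving the study treatment". Response at Week 65 is then derived from the imputed TFC score.

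Protocol 9.4.3 gives the same split. SAP 7.1.1 repeats it in slightly different words: "participants who discontinue the treatment due to disease progression-related death, or meet the Stopping Rules will be considered non-responders", whereas "participants who discontinue the treatment for other reasons will be imputed by hypothetical values from treatment discontinuation onward".

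SAP 7.1.1 also defines the intercurrent events for the trial, and death is listed there without any qualification as to cause: "treatment discontinuation due to, for example, death, AEs, progressive disease, or meeting Stopping Rules for QT/CrCl/psychiatric reasons". Protocol 7.2 likewise lists death, unqualified, among the reasons for discontinuing study drug.

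The rule is carried to other endpoints by reference. For CGI-C response, Protocol 9.4.3 says the endpoint "will be analyzed using a logistic regression in the mITT population, as described above for binary UHDRS-TFC response". SAP 7.4.3 says "Main estimands for binary endpoints will be similar to the main estimand for the binary UHDRS-TFC response".

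**The concern.** The endpoint is maintained or improved functional capacity at Week 65. A participant who has died cannot have that outcome, yet the written rule allows it to be recorded for some deaths.

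The ordering of outcomes is also inconsistent. A living participant taken off drug under a Stopping Rule is a certain non-responder. A participant who dies without first meeting such a rule, from a cause not attributed to progression, may be a responder.

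The progression-related category may catch few deaths. The participants are Stage 1 or 2, the main endpoint is at 65 weeks, and the SAP Preface describes an illness that generally lasts 15 to 20 years. Neither document says who decides whether a death is progression-related, or how.

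The p-value from this main estimand is the one used in the fixed sequence (SAP 7.4.3 and 5.6). TFC response is secondary endpoint 2, so it gates endpoints 3 to 9. CGI-C response is endpoint 9.

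**Working it through.** **1. Following a death through the rule**

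| Participant who dies before Week 65 | Handling in the main (mITT) estimand |
|---|---|
| No post-baseline in-clinic TFC (first scheduled at Week 26) | Not in mITT (SAP 4.1.2), so not analysed |
| Had met a Stopping Rule | Non-responder |
| Death judged progression-related | Non-responder |
| Stopped drug for another reason, gave a later TFC, then died | Fits neither branch of 7.4.2. SAP 7.1.1 omits the no-later-TFC condition and would impute. The two sections need reconciling |
| In mITT, other cause, no Stopping Rule met, no later TFC | Imputed under MAR as if on treatment; can be a responder |

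The last row is the problem.

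**2. Supportive estimands (SAP 7.4.2)**

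- 1 and 2 keep the same composite rule in the ITT population and impute the rest, 1 under MNAR and 2 under MAR. ITT also brings in deaths before any post-baseline TFC.
- 3 and 4 use observed data only, so a participant who died before Week 65 drops out.
- None counts every death as non-response.

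**3. Size for one arm**

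The plan states no response rate, death count or power for this endpoint. Its sample-size figures concern the primary mean change. They reproduce (372/0.775 = 480; 0.7 × 0.775 + 0.1 × 0.225 = 0.565) and do not bear on this point, except as a source of inputs.

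Inputs:

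- Annual TFC decline of 0.8 to 1.2 (Protocol 8.1.1). Over 65/52 = 1.25 years this is a mean change of −1.0 to −1.5.
- Assumed drug benefit of 0.7 and SD of 1.9 (SAP 3.3). With the benefit, the mean change is −0.3 to −0.8.
- SAP 7.2 rounds imputed TFC to the nearest integer. If that carries over to 7.4.2, response means an unrounded change of at least −0.5; if not, at least 0.
- Assumption, not in the documents: 1 to 5 deaths of this kind in an arm of 240, the planned arm size.

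Under a normal model for the imputed change, P(response) = 1 − Φ((c − m)/1.9), with c = −0.5 or 0:

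| Mean change m | Rounded (c = −0.5) | Unrounded (c = 0) |
|---|---|---|
| −0.3 | 0.542 | 0.437 |
| −0.8 | 0.437 | 0.337 |
| −1.0 | 0.396 | 0.299 |
| −1.5 | 0.299 | 0.215 |

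The probability therefore lies between about 0.2 and 0.55, against 0 if death were non-response. The overstatement is deaths × probability / 240:

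- Low end: 1 × 0.215/240 = 0.09 percentage points.
- High end: 5 × 0.542/240 = 1.13 percentage points.

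This is a group-level figure. The imputation conditions on a participant's earlier scores, so individual probabilities will differ.

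**4. Effect on the contrast**

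For illustration, take response rates of 55% and 45% among survivors, 240 per arm, and a credit of 0.5 per death. None of these comes from the documents. P-values are from an unadjusted log odds ratio and ignore between-imputation variance.

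| Deaths (active, placebo) | p, deaths imputed | p, deaths non-response |
|---|---|---|
| 3, 3 | 0.031 | 0.031 |
| 3, 0 | 0.030 | 0.042 |
| 5, 0 | 0.030 | 0.053 |

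With equal deaths nothing moves. With five against none, the same data cross 0.05, and the sequence would stop.

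**The case against.** The split is stated deliberately. SAP 7.1.1 uses progression-related death as its own example of a composite strategy, and the rule appears consistently in three places. A hypothetical strategy for an unrelated death is a definable estimand. That is fair, but it does not explain why a Stopping Rule in a living participant is failure while some deaths are not, and it leaves the attribution of cause undefined.

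Several stronger readings are tempting and are not supported:

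- *Every non-progression death is imputed as a possible response.* Section 1 of the working shows three groups for which the main estimand does not clearly do this. The scope of the Stopping Rules is also arguable: Protocol 7.1 includes the psychiatric rule, seizures and further cardiac and intracranial conditions under that heading, while SAP 7.1.1 names only QT, CrCl and psychiatric reasons. Some arrhythmia or suicide deaths may already be non-response.
- *A participant who has died will be scored a CGI-C responder.* The rule for intercurrent events carries over, but the only imputation model described treats TFC as a continuous variable. How CGI-C would be filled in is not stated.
- *The rule favours pridopidine.* It favours whichever arm has more such deaths, and the documents give no death data. Supportive Estimand 1 imputes from placebo data, which takes away the assumed on-drug benefit for active-arm deaths.
- *The effect is large.* SAP 3.6.3.1 reports a low discontinuation rate and 98.9% completion of in-clinic TFC. These are not death counts, but they suggest few imputed cases.

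**Conclusion.** The point holds for a defined group: mITT participants who die before Week 65 of a cause not attributed to disease progression, without having met a Stopping Rule and with no later TFC. As written, they are imputed as if still on treatment and can be responders on secondary endpoint 2. No planned analysis shows the result with all deaths as non-response.

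The expected size is small. On the assumptions of 1 to 5 such deaths in an arm of 240 and a response probability of about 0.2 to 0.55, that arm's rate is overstated by about 0.1 to 1.1 percentage points. The treatment comparison changes materially only if deaths are unequal and the p-value is near 0.05. The change is still worth making because the direction of the error is wrong, the endpoint gates seven others, and the correction is easy.

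**What to change.** By SAP addendum before database lock and unblinding, which SAP 5 provides for:

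- In the composite branch of 7.4.2 and 7.1.1, replace disease-progression-related death with death from any cause before the Week 65 assessment.
- Exclude death explicitly from the other reasons that are imputed under MAR or, in Supportive Estimand 1, MNAR.
- Carry the rule to CGI-C response and the other binary endpoints through 7.4.3, at their respective visits.

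The same addendum could reconcile the no-later-TFC condition between 7.4.2 and 7.1.1 and state how a missing CGI-C is imputed.

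The SAP prevails over the protocol (SAP Preface; Protocol 9), so a separate protocol amendment is not required; the Preface asks only that the difference be explained in the CSR. The cost is a few words and possibly slightly lower response rates. No new data are needed, and cause of death need no longer be attributed for this purpose.
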